#### **9.4.9 Injection site reactions**

Injection site reactions must be recorded on the AE form and the injection site reaction form. Signs and symptoms of injection site reactions include but are not limited to pain, numbness, itching, burning, redness, induration, swelling, dimpling, macula, haematoma and bleeding.

#### **9.5 Pharmacokinetics**

Concizumab will be quantified using a validated ELISA assay. Recombinant human TFPI will be used to capture concizumab. A colorimetric detection signal is obtained by the enzymatic reaction of horseradish peroxidase labelled anti-human IgG4 specific antibodies with the chromogenic substrate TMB (3,3',5,5'-tetramethylbenzidine). The amount of anti-TFPI present in the calibration, quality control and test samples correlate with the obtained signal strength.

Validation of the assay follows current guidelines for bioanalytical method validation. Bioanalytical data will be reported in a bioanalytical report.

The concizumab ELISA will be used to evaluate exposure and pharmacokinetics of concizumab.

For patients dosed with concizumab from visit 2a (patients in arms 2, 3 and 4), two 24-hour PK/PD-sessions will be conducted at visits 2a and 9a. The concizumab dose will be administered in the abdomen and blood samples will be drawn pre-dosing, 3, 6, 9 and 24 hours after dosing. Care must be taken to ensure the 24-hour sample is drawn before the next daily dose of concizumab is administered. At the day of visit 9a patients should not dose themselves at home; the dose will be administered at site followed by blood sampling. The dose should be taken at site in the abdomen and care must be taken to ensure the 24-hour sample is drawn before the next daily dose of concizumab is given.

For patients who had a 24-hour PK profile measured at visit 2 prior to the treatment pause, a new 24-hour PK profile at visit 2a should not be conducted after restart of the trial. For these patients, only pre-dose and 24-hour post-dose samples should be taken at visit 2a. Care must be taken to ensure the 24-hour sample is drawn before the next daily dose of concizumab is administered.

Following items must be recorded in the eCRF:

- Time of lab samples taken
- Time of concizumab dose
- Injection site location

See Section [2.1](#) for the specific timepoints for the PK analysis.

In addition to the two PK/PD sessions, pre-dose concizumab levels ( $C_{trough}$ ) will be measured throughout the concizumab treatment period. These blood samples must be drawn prior to trial product administration as specified in the flowchart in Section [2](#). If the patient has taken the daily

dose of concizumab before collection of the concizumab ELISA sample, then visit 4a (arm 2, 3, 4) and visit 9a.2 (arm 1) should be rescheduled.

## 9.6 Pharmacodynamics

Pharmacodynamics assessments Thrombin Generation, and Free TFPI are described in Section [9.2.7](#) For patients dosed with concizumab from visit 2a (patients in arms 2, 3 and 4), two 24-hour PK/PD-sessions will be conducted at visits 2a and 9a; see Section [9.5](#) for further details.

## 9.7 Human Biological Specimen for storage

### 9.7.1 Genetics

Whole blood samples for DNA genotyping will be collected according to the flowchart in Section [2](#) for future analysis and long-term storage from patients who have consented to participate in this part of the trial. Participation in the genetic research is optional. Patients who do not wish to participate in the genetic research may still participate in the trial.

In the event of sample handling failure, a replacement genetic blood sample may be requested from the patient.

Genetic samples will not be evaluated by the investigator.

Patients who had a sample taken at visit 1 before the treatment pause should not have that sample re-taken upon trial restart.

Please refer to [Appendix 9](#) for further information regarding the genetic research. Details on processes for collection, shipment and destruction of these samples can be found in the laboratory manual.

### 9.7.2 Biomarkers

Serum and plasma samples will be collected according to the flowchart in Section [2](#) for future exploratory laboratory analysis and long-term storage from patients where additional consent has been obtained. Patients who do not wish to participate in this research may still participate in the trial.

Biomarker samples will not be evaluated by the investigator.

Patients who had a sample taken at visit 1 before the treatment pause should not have that sample re-taken upon trial restart.

Please refer to [Appendix 9](#) for further information regarding the biomarker research and details on processes for collection, shipment and destruction of these samples can be found in the laboratory manual.

## 9.8 Health economics

A set of eDiary screens assembled in a monthly diary will be made available to the patient every 30 days. The screens are designed to collect:

- Number of school or workdays missed

- Number of days where a patient used an aid to move around
- How many days in-home professional nursing was needed.

The monthly diary will be completed by the patient in the eDiary.

## 9.9 Surgery

Minor surgical procedures are allowed during the trial (for surgery definitions see [Table 14](#)). Planned major surgery is not allowed.

Local/topical use of antifibrinolytics e.g. tranexamic acid is allowed. Use of single systemic doses is allowed after careful benefit-risk evaluation.

During the perioperative period patients should continue daily concizumab prophylaxis.

**Table 14     Surgery definitions**

| Category              | Definition                                                                                                                             | Examples                                                                                                                                                                                                                                                                             |
|-----------------------|----------------------------------------------------------------------------------------------------------------------------------------|--------------------------------------------------------------------------------------------------------------------------------------------------------------------------------------------------------------------------------------------------------------------------------------|
| Major surgery: | Any invasive operative procedure that requires $\geq 3$ doses of bypassing therapy and/or where any one or more of the following occur | A body cavity is entered
A mesenchyme barrier (e.g. pleura, peritoneum or dura mater) is crossed
A fascia plane is opened
An organ is removed
Normal anatomy is operatively altered                                                                                      |
| Minor surgery: | Any invasive operative procedure where only the skin, the mucous membranes or superficial connective tissue is manipulated             | Implanting of central venous access devices (ports, central venous catheter, pumps and other central venous access devices) in subcutaneous tissue
Skin biopsies
Simple dental procedures
Ear tube/drain insertion
Circumcision
Port insertion in paediatric patients |

For surgery the following should be recorded in the eCRF:

- Type of Surgery
- Data and stop time and dose of preventive treatment (haemostatic medication).
- Other treatments during surgery (concomitant medication)
- Indication of surgery
- Anatomical Location of surgery
- Date of surgery
- Start and stop time of surgery

In the instance of acute major surgery, it is recommended to pause concizumab at the discretion of the investigator.

## 10 Statistical considerations

### 10.1 Sample size determination

The estimand for the primary endpoint will for patients in arms 1 and 2 be addressed based on the Full Analysis Set (FAS; see Section [10.2](#)) using negative binomial regression.

The sample size calculation has been determined based on the above estimand. In the calculation the treatment duration is set to 24 weeks for patients in arm 1 and 32 weeks for patients in arm 2. Of note, expected differences in observation periods and efficacy in patients exposed before the pause is not accounted for in the sample size calculations.

The trial will be powered for confirming superiority of the concizumab prophylaxis versus no prophylaxis (on-demand) using a significance level of 5%.

The power for concluding superiority of concizumab prophylaxis over no prophylaxis (on-demand) treatment for the estimand is at least 88% having 42 patients, allocated in a 2:1 manner to either concizumab prophylaxis (n=28) or no prophylaxis (on-demand) (n=14) to the trial and assuming a yearly overdispersion of 13, an ABR of 18 during on demand treatment and an ABR of 3 to 5 on the new concizumab regimen.

#### ABR assumptions

For the on-demand inhibitor patients, an average ABR of 18 is considered appropriate, based on previous trials ([Table 15](#)).

**Table 15 Annualised bleeding rate assumptions for inhibitor patients treated on-demand**

| Regimen   | Compound  | Study                    | N  | ABR              |
|-----------|-----------|--------------------------|----|------------------|
| On-demand | Novoseven | NN1731-3562 a | 72 | 17.1             |
|           | Novoseven | NN7128-1907 b | 23 | 29.8             |
|           | Novoseven | NN7025-3601 c | 51 | 7.9 e |
|           | NovoSeven | NN7415-4310 d | 9  | 21               |

aNN1731-3562 CTR. bNN7128-1907 CTR. cNN7025-3601 CTR. dNN7415-4310 (explorer 4) main part internal result meeting presentation. eThe ABR is estimated: mean number of bleeding episodes per patient per 19.6 months ((12.9/19.6)\*12=7.9).

Also, considering a FEIBA® median ABR 28.7 in the on-demand arm of the randomised FEIBA® prophylaxis trial, an assumed ABR of 18 seems reasonable and conservative for the inhibitor on-demand population. An ABR for concizumab prophylaxis of approximately 3–5 bleeds/year is expected.

#### Over-dispersion assumptions

A yearly over-dispersion of 13 is deemed realistic based on experience from previous trials.

## Power

Assuming an ABR of 18 for the on-demand arm and an ABR between 3 and 7 for the concizumab arm (arm 2), a yearly over-dispersion varying between 11 and 15 and performing 10,000 simulations of each group will produce different scenarios of power for superiority tabulated in [Table 16](#) below.

**Table 16 Power for superiority for 42 patients randomised 2:1 assuming an ABR for the on-demand treatment of 18**

| Power          | Yearly over-dispersion |     |     |
|----------------|------------------------|-----|-----|
| ABR concizumab | 11                     | 13  | 15  |
| 3              | 98%                    | 97% | 94% |
| 4              | 96%                    | 93% | 90% |
| 5              | 92%                    | 88% | 83% |
| 6              | 86%                    | 80% | 75% |
| 7              | 78%                    | 70% | 65% |

When evaluating the power of the negative binomial analysis with logarithm of exposure time as offset and treatment as factor, annual bleeding rates of 18 and 3-5 are assumed for the on-demand patients and concizumab exposed patients, respectively. Assuming further a yearly over-dispersion of 13, the power for concluding superiority of concizumab prophylaxis becomes at least 88% with 28 patients in the concizumab arm and 14 in the comparator arm.

## Expected withdrawal pattern

Since treatment options for haemophilia patients with inhibitors are limited, the completion rate for this trial is expected to be high with less than 17% withdrawing or discontinuing treatment prematurely. In order to account for potential withdrawal patients, in particular in relation to other endpoints in this trial, a total of 51 patients will be randomised to ensure a high likelihood of having at least 42 patients completing arms 1 and 2.

### 10.2 Definition of analysis sets

- Safety analysis set (SAS): All patients exposed to concizumab PPX or randomised to OnD.
- Full analysis set (FAS): All patients randomised to concizumab PPX or OnD or allocated to arm 3 or 4.

### 10.3 Statistical analyses

The statistical analysis plan (SAP) was updated prior to the first patient restarting the trial, to reflect the changes made in protocol amendment #4, and includes a more technical and detailed elaboration of the statistical analyses.

As described in Section [5.1](#), several evaluations will be made prior to the end of this trial. This section will describe the analyses of the primary and key secondary endpoints at the primary analysis cut-off focusing on arms 1 and 2

The bleed rate is defined as the number of treated bleeds over the respective observation periods. As a general rule, a treated bleed is defined as any bleed where a factor-containing product is reported between the start and stop time of a bleed. Multiple bleeding locations occurring at the same time

point will be counted as one bleeding episode. Further, the endpoints will not include re-bleed. A re-bleed is defined as a bleeding episode (worsening of bleeding site conditions e.g. swelling, pain) starting within 72 hours after stopping treatment of a previous treated bleeding episode (or re-bleed) at the same anatomical location. Note that there can be more than one re-bleed related to the same bleed. If a bleeding episode occurs in the same location more than 72 hours after stopping treatment of a previous bleeding episode (or re-bleed) in the same location, the bleed is defined as a new bleeding episode.

The significance level is 5%. The primary endpoint is analysed using negative binomial regression. Superiority of concizumab prophylaxis over no prophylaxis will be concluded if the two-sided 95% confidence interval of the treatment ratio is below 1.

In order to maintain the type 1 error for the key secondary endpoints, the hypotheses related to bleeds, SF36v2 physical functioning and SF36v2 bodily pain endpoints will be subject to a hierarchical testing. If a hypothesis is confirmed, the significance level will be reallocated to the next hypothesis in the hierarchy and then that hypothesis will be tested at the 5% significance level. This process will be repeated until no further hypotheses can be confirmed. All three tests will be for superiority hypotheses. The order of the hierarchy will be the primary endpoint followed by change from baseline in SF36v2 Bodily pain followed by the change from baseline in SF36v2 Physical functioning.

### **10.3.1 Primary endpoint**

The primary endpoint is defined in Section [4.3.1](#).

‘The estimand associated with this endpoint will be addressed comparing the number of treated bleeds between arms 1 and 2 based on the FAS using negative binomial regression with the patient’s number of bleeds analysed as a function of the randomized treatment regimen, type of haemophilia (HAWI or HBWI) and bleeding frequency (<9 or  $\geq$  9 bleeding episodes during the past 24 weeks prior to screening) and the logarithm of the length of the observation period included as an offset in the model. For this analysis patients will contribute as follows:

- in arm 1 with the observation period from randomisation to start on the new concizumab dosing regimen in the extension part or permanent treatment discontinuation
- in arm 2 (exposed to the new concizumab dosing regimen) with the observation period from start on the new concizumab dosing regimen until the primary analysis cut off or permanent treatment discontinuation
- in arm 2 (patients who has not restarted) with the observation period from the start of the initial dosing regimen until permanent treatment discontinuation

The primary analysis will also account for the different intercurrent events as described in the estimand.

From the statistical model, an estimate of the rate ratio of the ABR between the treatment regimens (concizumab prophylaxis and no prophylaxis) with corresponding 95% confidence interval and a p-value for the test for superiority will be provided. Also, estimates of the actual ABRs with corresponding 95% confidence intervals will be provided for arms 1 and 2. To the extent the statistical model allows, separate estimates for HBWI and HAWI will be provided.’

## Sensitivity analyses

The below sensitivity analyses will be implemented to further investigate the different assumptions that go into the above estimand and statistical methodology. Note that as different strategies are implemented to address some of the intercurrent events, these analyses address a slightly different estimand.

- The number of treated bleeds will be analysed with a multiple imputation technique where the number of treated bleeds for patients that are not exposed to the new concizumab dosing regimen are imputed based on treated bleeds observed on the initial dosing regimen. The imputation technique and inference drawn will be based on the methods detailed by Keene et al (2014).
- A tipping point analysis using a similar method as described above. Patients only exposed to the initial dosing regimen of 0.25 mg/kg/day will be modelled with an increasing bleeding rate until the conclusion of superiority is changed. The data used will be the same as in the primary analysis and the offset period will be kept fixed within this analysis
- The primary analysis will also be repeated using all concizumab exposure in arm 2 up until the primary analysis cut-off, irrespective of the dosing regimen. Hence, in this sensitivity analysis the initial and the new concizumab dosing regimen are both included (to maximise the amount of data used) and compared with arm 1 (OnD).
- A statistical analysis using a model similar to the one used for the primary analysis but including an interaction term between treatment and a factor differentiating between patients randomised before and after the pause will be performed.
- In order to investigate the effect of excluding observed data a model where all intercurrent events will be handled by use of the treatment policy strategy will be fitted. The model will be similar to the primary analysis but where the patient's bleeds and observation time collected post permanent treatment discontinuation (the first intercurrent event) and collected during periods with unallowed use of factor products not related to treatment of a bleed (the third intercurrent event) will be used. This analysis will be performed using the FAS.
- In order to not rely on the model assumptions of the primary analysis a non-parametric Van Elteren test to compare the mean ABR in the two randomised groups will be done. This is done using the FAS where patients contribute with observation time as described under Section [10.3.1](#).

Further sensitivity analyses can be specified in the SAP.

### 10.3.2 Secondary endpoints

#### 10.3.2.1 Key secondary endpoints

The key secondary endpoints are defined in Section [4.3.2.1](#).

The two key secondary endpoints based on SF-36v2 will be analysed including all patients in the FAS where patients contribute with observation time as described under Section [10.3.1](#). In order to incorporate the patients from the original randomisation that have not restarted, statistical analysis will be implemented as a statistical model using multiple imputations where the subjects without any available SF-36v2 measurements at scheduled visits will have their SF-36v2 value imputed from the available information from the treatment group the subject has been randomised to. For

subjects that have no observations on the new dosing regimen, the baseline value before the initial randomisation will be used. Subjects without any post-randomisation measurements contribute to the analysis, as the missing values will be imputed. The analysis will be implemented as follows.

- For all patients the baseline value will be set to either the value obtained just prior to the re-start and if that is missing, the value prior to the initial randomisation.
- In the first step, intermittent missing values are imputed using a Markov Chain Monte Carlo method, in order to obtain a monotone missing data pattern. This imputation is done for each treatment group separately and 1000 copies of the dataset will be generated.
- In the second step, for each of the 1000 copies of the dataset, an analysis of variance model with stratification factors as factors and baseline SF-36v2 value as covariate is fitted to the change in SF-36v2 from baseline to week 4 for each treatment group separately. The estimated parameters, and their variances, from these models are used to impute values at week 4 for subjects in each treatment group, based on stratification factors and baseline SF-36v2.
- In the third step, for each of the 1000 copies of the dataset, missing values at week 8 are imputed in the same way as for week 4 but now also including the SF-36v2 values at week 4 in the model. This stepwise procedure is then repeated sequentially for week 16 and 24 and in each step the SF-36v2 values in previous weeks are also included in the model.
- For each of the complete data sets, the change from baseline to week 24 is analysed using an analysis of variance model with treatment and stratification factors as factors, and baseline SF-36v2 as a covariate.

The estimates and standard deviations for the 1000 data sets are pooled to one estimate and associated standard deviation using Rubin's rule. From these the 95% confidence interval for the treatment difference is calculated together with a p-value for the test of superiority.

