### 4.3.2 Secondary endpoints

#### 4.3.2.1 Key secondary endpoints

| Endpoint title                        | Time frame                                                   | Unit  |
|---------------------------------------|--------------------------------------------------------------|-------|
| Health economics               |                                                              |       |
| Change in SF36v2 bodily pain          | From start of treatment (week 0 a ) until week 24 | Score |
| Change in SF36v2 physical functioning | From start of treatment (week 0 a ) until week 24 | Score |

aDefined as time of randomisation to on-demand administration or time of start of the new concizumab dosing regimen

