### Treatment arms 1 and 2:

Approximately 51 patients (27 HAwI and 24 HBwI), previously treated on-demand, will be randomised 1:2 to no prophylaxis versus concizumab prophylaxis. Patients will be stratified by the haemophilia type and the bleeding frequency.

**Patients randomised to arm 1 before the pause** were instructed to continue their on demand treatment and report data until trial restart. It is expected that all of these patients will have completed at least 24 weeks of on demand treatment when restarting the trials. Upon completion of the main part, the arm 1 patients will start the new concizumab dosing regimen (see Section [5.2.1](#)) and receive up to 136 weeks of concizumab PPX in the extension part of the trial.

**Patients randomised to arm 2 before the pause** have discontinued their concizumab treatment and received available standard of care during the pause. Upon restart, patients who do not fulfil any discontinuation criteria (see Section [8](#)) will receive the new concizumab dosing regimen from visit 2a (described in Section [5.2.1](#)).

**New patients eligible for arms 1 and 2** will be recruited to fulfill the protocol target numbers. New patients eligible for arms 1 and 2 will be randomised as outlined in Section [7.2](#).

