#### Patients who were enrolled before the pause

Patients who were randomised or allocated to treatment in this trial before the pause, should re-enter the trial as outlined in [Table 1](#)

**Table 1** Visit overview for patients restarting this trial

| Allocation before the pause | Allocation at restart |
|-----------------------------|-----------------------|
| Arm 1                       | Arm 1 - visit 9a      |
| Arm 2                       | Arm 2 - visit 2a      |
| Arm 3                       | Arm 3 - visit 2a      |
| Arm 4                       | Arm 4 - visit 2a      |

Note: Visit 9a is the first visit in the extension part for arm 1. At visit 9a, the patients in arm 1 will start concizumab PPX.

[Table 2](#) below summarises the expected numbers of randomised/enrolled patients in each arm. In total 136 patients are expected to be enrolled; this includes patients enrolled before as well as after the pause. The aim is to have approximately 15 unique HAwI and HBwI adolescent patients defined as patients between  $\geq 12$  to  $< 18$  years at trial start.

**Table 2** Randomisation/enrolment overview

[figure not shown]
|      | Number of patients randomised/enrolled |       |          |                             |
|------|----------------------------------------|-------|----------|-----------------------------|
|      | Arm 1                                  | Arm 2 | Arm 3    | Arm 4
(PPX or on-demand) |
| HAwI | 9                                      | 18    | Up to 15 | 60                          |
| HBwI | 8                                      | 16    | Up to 10 |                             |

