### 5.2.2 On-demand treatment

Patients in arm 1 will continue on-demand treatment with their usual bypassing product until visit 9 (end of main part for arm 1). Patients included prior to the treatment pause will re-start the trial at visit 9a; see Section [5.1](#). Novo Nordisk will not provide or reimburse on-demand treatment for patients in arm 1. In the extension part, patients in arm 1 will receive daily concizumab subcutaneous injections (see Section [5.2.1](#)).

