### 9.2.6 Patient-reported outcome questionnaires

This trial includes eight Patient-Reported Outcome (PRO) questionnaires, see [Table 12](#).

PRO questionnaires will be completed, if available in local language, by the patient (not the caregiver) in accordance the trial flow chart in Section 2. PRO-questionnaires will be completed as ePROs by the patient using the same eDiary except for Haem-A-QoL (all countries) and PROMIS (some countries) which will be completed on paper.

At visit 2a and visit 9a, patients must complete the PRO questionnaires on the day of the site visit, preferably before any other assessments. For the remaining visits, patients should preferably complete the PRO questionnaires on the day of the visit before any other assessments.

Patients re-entering the trial after the treatment pause should fill out all forms according to the flowchart in Section 2. For these patients, previous treatment will be defined as the treatment they received during the concizumab treatment pause. The site staff must inform the patients about this 'previous treatment' definition prior to completing the questionnaires.

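### The SF-36v2 baseline rule is not split by arm and, as written, gives on-demand patients randomised before the pause a baseline at or after their week-24 outcome.

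*Protocol*

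**What the plan says.** Protocol Section 10.3.2.1 analyses change in SF-36v2 bodily pain and physical functioning from baseline to week 24, with baseline as covariate and sequential multiple imputation at weeks 4, 8, 16 and 24. Its baseline bullet reads: "For all patients the baseline value will be set to either the value obtained just prior to the re-start and if that is missing"; its fallback is the value before the initial randomisation. The imputation model in the next steps is "fitted to the change in SF-36v2 from baseline to week 4 for each treatment group separately".

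A sentence just before the bullets says that for "subjects that have no observations on the new dosing regimen, the baseline value before the initial randomisation will be used".

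Section 4.3.2.1 measures both endpoints from week 0 to week 24. Footnote a gives week 0: "Defined as time of randomisation to on-demand administration or time of start of the new concizumab dosing regimen".

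On the restart, Section 5.1 expects that "all of these patients will have completed at least 24 weeks of on demand treatment when restarting the trials", speaking of arm 1 patients randomised before the pause. Table 1 there ("Visit overview for patients restarting this trial") sends those patients to visit 9a, described as their first extension visit. Section 5.2.2 agrees: "Patients included prior to the treatment pause will re-start the trial at visit 9a". Section 9.2.6 adds: "At visit 2a and visit 9a, patients must complete the PRO questionnaires on the day of the site visit".

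**The concern.** The bullet covers every patient and makes no exception for arm 1. The protocol uses the word re-start for arm 1 as well as for the concizumab arms. For an on-demand patient randomised before the pause, the last SF-36v2 value before re-start is the visit 9 value, which is the week-24 outcome itself, or a later value at visit 9a. Read as written, baseline is at or after the outcome.

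Bodily pain and physical functioning are the only endpoints tested after the primary in the 5% hierarchy (Section 10.3). If the bullet is followed, the affected patients' change is pulled towards zero, a post-outcome value becomes the covariate, and the same value enters the week-4 imputation model. The resulting bias in the treatment difference can go either way.

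**Working it through.** **Timing and consistency**

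1. Arm 1 patients randomised before the pause re-start at visit 9a (Section 5.1, Table 1; Section 5.2.2).
2. They are expected to have at least 24 on-demand weeks by then, and visit 9 ends their main part. A late entrant could fall short: 31 March to 31 August 2020 is 153 days, or 21.9 weeks. That value would still be post-randomisation.
3. The fallback would seldom apply. Questionnaires are required at visit 9a, and the pre-pause schedule in Appendix 12 has SF-36v2 at visits 2, 4, 5, 7 and 9.
4. So the literal baseline conflicts with week 0 in Section 4.3.2.1. A change from baseline to week 4 also has no meaning when week 4 comes before the baseline.
5. The week-56 SAP, Section 5.1, sets the arm 1 on-demand baseline before randomisation. It is descriptive only, but it shows that the sponsor elsewhere splits baseline by arm.

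**Size**

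The plan has no figure to reproduce. Arm sizes 17 and 34 come from Table 2. The number affected (x), the SD, the baseline-to-week-24 correlation (rho) and the on-demand change are not in the documents. Assumed here: x = 4 or 9, SD 10, rho 0.6 to 0.7, higher score better.

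If x arm 1 patients have their week-24 value as baseline, their change is 0 and their outcome-on-baseline slope is 1. The pooled slope is about

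slope = (rho × (51 − x) + x) / 51

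and the arm 1 baseline mean shifts by (x/17) × on-demand change, so

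bias = slope × (x/17) × on-demand change.

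| x | rho | slope | bias per point of on-demand change |
|---|---|---|---|
| 4 | 0.6 | 32.2/51 = 0.63 | 0.15 |
| 4 | 0.7 | 36.9/51 = 0.72 | 0.17 |
| 9 | 0.6 | 34.2/51 = 0.67 | 0.36 |
| 9 | 0.7 | 38.4/51 = 0.75 | 0.40 |

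At a change of +3 and rho 0.7 the bias is 0.51 (x = 4) or 1.20 (x = 9).

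A simulation used 6000 replicates per cell and an ANCOVA of change on treatment, baseline and two balanced, non-prognostic strata factors, two-sided 5%. The affected baselines were replaced by the week-24 value or by a later value correlated 0.8 with it.

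| Scenario | Correct baseline | x = 4 | x = 9 |
|---|---|---|---|
| Both arms 0: bias | 0 | 0 | 0 |
| Both arms 0: one-sided false superiority (nominal 2.5%) | – | 2.0–2.4% | 1.4–2.5% |
| Both arms +3: bias | 0 | 0.4–0.6 | 1.0–1.2 |
| Both arms +3: one-sided false superiority | 2.2–2.6% | 3.2–4.6% | 5.5–8.0% |
| On-demand −3, concizumab +2: estimate (true 5) | 5 | about 4.5 | 3.8–4.0 |
| On-demand −3, concizumab +2: power | 53–63% | 47–57% | 38–46% |

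If all 17 were affected with no mean change, and one value served as both baseline and outcome, the false-superiority rate would be 0.6%.

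A smaller run added by-arm sequential imputation (rho 0.7, 10 copies, Rubin's rule, 1200 replicates) and gave the same pattern. With both arms at +3, false superiority was 2.1% (x = 0), 3.7–3.8% (x = 4) and 6.7–7.1% (x = 9). With changes −3/+2, power was 52%, 46–49% and 36%.

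A separate simulation at rho 0.6 with x = 8 and on-demand change of −3 or +3 estimated a true difference of 8 as 7.04 and a true difference of 2 as 2.96. The formula gives (33.8/51) × (8/17) × 3 = 0.94, that is 7.06 and 2.94.

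**The case against.** The strongest reply is that the rest of the plan already settles arm 1. Section 10.3.2.1 refers to Section 10.3.1 for contributing time, and arm 1's period there ends when the new regimen starts. Within that period every arm 1 patient has no observations on the new regimen, so the sentence before the bullets would give them the pre-randomisation value. Footnote b of the Section 2 flowchart also equates week 0 with trial restart. On that meaning, pre-pause arm 1 patients, who skip visit 2a, have no re-start value and the fallback applies. Finally, a baseline after the outcome is so unworkable that the sponsor can hardly have meant it.

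Part of this stands. A sensible reading exists, and the sponsor may have had only arm 2 in mind. But the sentence before the bullets follows text on patients who did not restart and does not name arm 1, while pre-pause arm 1 patients do start the new regimen at visit 9a. Footnote b does not override Table 1, which places arm 1's re-start at visit 9a. The questionnaire rows of the Section 2 flowchart cannot be read in the text available, but a visit 9 value alone would be enough to block the fallback.

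It is also fair that the error rates rest on assumed inputs, and that these tests take place only if the primary succeeds. The primary-cut-off SAP, to which the supplied SAP refers for the main-part analyses, may already state the right rule.

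**Conclusion.** The concern holds: the rule is wrong as written for arm 1 patients randomised before the pause, and it contradicts the endpoint definition. It should be fixed. New patients, restarted arm 2 patients, patients who did not restart and the primary endpoint are not affected.

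The harm depends on the number affected and on the mean on-demand change, neither of which is given. With no mean on-demand change there is no bias and the test is, if anything, conservative. If on-demand patients improve, the bias favours concizumab; if they worsen, the effect is understated and power is lost. Under the assumptions above, the bias is 0.15 to 0.17 point per point of on-demand change with 4 of 17 affected, and 0.36 to 0.40 with 9 of 17. Confidence is medium, because the primary-cut-off SAP was not available.

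**What to change.** Replace the baseline bullet in Section 10.3.2.1 with a rule by arm:

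- Arm 1: the last SF-36v2 value before randomisation.
- Arm 2: the last value before the first dose of the new regimen; if that is missing, or if the patient did not restart, the value before the initial randomisation.

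Then confirm that the primary-cut-off SAP states the same rule. This agrees with Section 4.3.2.1 and the week-56 SAP, and leaves arm 2 and non-restarters as they are. The cost is one sentence. No new data are needed, because SF-36v2 was already scheduled at visit 2 before the pause (Appendix 12).
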